## 5. Inclusion/Exclusion Criteria

Inclusion criteria	Exclusion criteria

 
• age 65 years or older
 
• able to read and write English
 
• cLBP that has persisted at least 3 months and pain on at least half of the days for the previous 6 months
 
• average intensity of pain <math>\geq 4</math> on a 11-point numerical pain scale in the previous week
 
• have intact cognition (Mini-Mental State Examination, MMSE <math>> 24</math>)
 
• willing to commit to 4-weekly study visits and up to 12-months follow-up.
 
• able to apply pressure to the seeds with tapes on their ears
 
	
 
• malignant or autoimmune diseases (e.g., rheumatoid arthritis)
 
• known acute compression fractures caused by osteoporosis, spinal stenosis, spondylolysis, or spondylolisthesis because these conditions may confound treatment effects or the interpretation of results
 
• sciatica with leg pain greater than back pain
 
• allergy to the tape
 
• use of some types of hearing aids (size may obstruct the placement of seeds)
 
• pain in other parts of the body that is more severe than the cLBP and which occurs daily or almost every day with at least moderate intensity or acute pain; neurological disorders that could interfere with pain reporting or confound performance on the other outcomes, cerebral tumor, Alzheimer's disease (or other cognitive illnesses), prior stroke, or multiple sclerosis
 

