### c. Statistical plan including sample size justification and interim data analysis.

The primary outcomes are measured at 1-month post-completion of treatment. In our pilot study (i.e., pain intensity, pain interference, and physical function), Cohen's d (the effect sizes in terms of the standardized difference) ranged from 0.65 (physical function) to 1.28 (pain intensity) between the APA and the sham APA one month after intervention. Our pilot sham group (CG 1, non-reactive points) should have similar or better outcomes than CG 2 (enhanced usual care). The power calculation is based on the smallest observed effect size of 0.65 for a more conservative estimate for the sample size required in this proposed study to detect a difference between the active intervention and either of the control conditions. With 150 participants (50 participants in each of the three groups), we will be able to achieve 90% power to detect an effect size of .65 (between the APA and either of the CG arms) at a two-tailed significance level of 0.05. We anticipate that approximately 10% will be lost to follow-up at 1-month (primary endpoint) based on our pilot study (10% dropout at 1-month follow-up after 4-week APA), and [name] R01 (11% after 5 months follow-up). We plan to recruit 200 participants to allow for an adequate sample size in our exploratory analysis of the 12-month follow-up, assuming 25% of the enrolled sample will be lost to follow-up at 12-months. Achieving this sample size during a 42-months accrual period will require enrolling 58 participants per year, which should be feasible through our proposed recruitment strategies. With this sample size, we will be able to detect significant changes in some of the biomarkers (CGRP) but not all based on our pilot studies. We are collecting these to get a better estimate of the effect using a larger sample size.

Analysis plan for aim 1 will be to determine the efficacy of APA for cLBP at one month post treatment. For continuous outcomes, we will use a general linear mixed model (GLM) to construct a multilevel model for comparing the differences in the change in the outcomes from baseline to one month among the three groups. The group-by-time interaction is the main parameter of interest. This model will adjust for fixed

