effects from important demographic and clinical covariates, if needed. Random effects from subject heterogeneity and temporal autocorrelation with the first-order autoregressive (AR(1)) covariance structure will be used to model the repeated measurements. The comparison of all outcome measures between, before, and after APA will assess possible treatment placebos (i.e., point specificity) and blindness of intervention. In addition to reporting mean score changes of outcomes reaching clinical significance, a cut point of 30% improvement for primary outcomes will be used for responder analysis. For responder analysis of primary outcomes, we will adopt a generalized logistic mixed model with the same fixed and random effects and AR(1) covariance structure. In both models, violation of assumptions will be detected by corresponding model diagnostics. Using the approach outlined above, analyses will be conducted using the monthly data through 12 months to explore the maintenance of the effect over time. Quadratic terms will be included in the model to allow for non-linear change across time.

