Analysis for aim two, evaluating the effect of APA on biomarkers, the analytical strategies for Specific Aim 1 will be used. Outcomes at one-month post treatment will be examined using each biomarker individually and two latent variables with pre-defined biomarkers within the groups of pro- and anti-inflammatory biomarkers. We hypothesize that the analgesic effects of APA are the aggregating and counter-interacting effects of different biomarkers within each latent variable. Before analysis, we will check the normality assumption in original data and log-transformed data. If normality cannot be met in both types of data, we will use two alternative approaches: we will apply a non-parametric test (e.g., Kruskal-Wallis test) to do multiple comparisons in each time difference among three groups; We will categorize the change of biomarker measurement into increase (recoded as 1) and decrease (recoded as 0) from baseline, and apply a GLM, which can handle repeated measurements and subject heterogeneity. To examine the sustained effect of the intervention over time in biomarkers (baseline, 1, 3, 6, 9, 12 months), we will use the approach described in Aim 1 using linear mixed models with quadratic terms to model the change in biomarkers across time. Each biomarker will be tested individually and the two latent variable within pro- and anti-inflammatory biomarkers as well.

Aim three analyses will examine the moderating effects of demographics, comorbid conditions, treatment, and placebo effects, as well as the mediating effects of biomarkers in both primary and secondary outcomes. To examine whether or not demographics, comorbid conditions, and placebo effects moderate the relationship between APA treatment on primary and secondary outcomes, the previously described regression models in Specific Aim 1, which include the main effect terms for the intervention or group, will be

expanded to include the main effect terms for moderators and the three-way interaction terms between group, time, and moderators. Models will be simultaneously estimated under a framework of a mixed model structure by adding a covariance structure to consider possible correlations among biomarkers.

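### The Aim 1 primary contrast is in effect an unadjusted change from baseline: valid and unbiased, but less precise than adjusting for a baseline score already collected

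*Combined protocol and SAP*

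**What the plan says.** All of this is in the combined protocol and SAP, mainly section 7c.

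- **Target.** The Aim 1 model is for "comparing the differences in the change in the outcomes from baseline to one month among the three groups", and "The group-by-time interaction is the main parameter of interest".
- **Group effect.** The Aim 3 text describes the Aim 1 models as ones "which include the main effect terms for the intervention or group". Nothing constrains the arm means to be equal at baseline.
- **Covariates.** The model adjusts for "effects from important demographic and clinical covariates, if needed". The baseline value of the outcome is not named.
- **Covariance.** Subject random effects plus AR(1).
- **Power.** 50 per group gives 90% power for a standardised difference of 0.65, two-sided 5%. Whether the SD is that of the 1-month score or of the change is not stated. Expected loss is "approximately 10% will be lost to follow-up at 1-month (primary endpoint").
- **Enrolment.** Section 7c gives 200. The sample-size text under Study Site in section 4 gives 270 (90 per group).
- **Sustained effect.** For clinical outcomes through 12 months, "Quadratic terms will be included in the model to allow for non-linear change across time". For biomarkers: "To examine the sustained effect of the intervention over time in biomarkers (baseline, 1, 3, 6, 9, 12 months"), also with quadratic terms.

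**The concern.** In a randomised trial the arms share a common expected baseline. A model that leaves each arm's baseline mean free and then targets the change subtracts the whole of each participant's baseline score, noise included. Adjusting for baseline subtracts only the part that predicts follow-up. Both are unbiased, but the second has a smaller standard error. The data are already planned, so the plan gives up precision on its primary comparison for nothing in return.

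The secondary point concerns the sustained-effect models. The documents expect a quick change and then near-maintenance. The Abstract's pilot reports 40% less pain one day after starting and 44% after four weeks, held at 1 month. The sample-size text in section 4 assumes 90% of the effect remains at 12 months. A single quadratic that starts at baseline cannot follow that shape. It would understate the early difference and place the peak months after treatment ended.

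**Working it through.** **1. The plan's own figure.** With d = 0.65, two-sided 0.05 and 50 per group, power is 0.901 (normal) or 0.896 (noncentral t). Enrolment: 150/(1 - 0.25) = 200. Both reproduce.

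**2. What the interaction estimates.** In simulated three-arm data with two visits and no missing values, the mixed-model interaction with a free group effect was -0.9729 (SE 0.2005). The raw difference in mean change was the same, with the same SE. Analysis of covariance on the same data gave SE 0.1666. Adding baseline as a main effect while it stayed in the response left the interaction unchanged.

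**3. Variance ratio.** Let rho be the correlation between baseline and 1 month. The documents give no legible value, so the range is assumed. With equal SDs, Var(change) is proportional to 2(1 - rho) and Var(adjusted) to 1 - rho². The ratio is 2(1 - rho)/(1 - rho²) = 2/(1 + rho).

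| rho | 0.3 | 0.4 | 0.5 | 0.7 |
|---|---|---|---|---|
| ratio | 1.54 | 1.43 | 1.33 | 1.18 |

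- Weekly visits, random intercept plus AR(1) and 10% loss: 1.47, 1.38, 1.29 at rho 0.32, 0.42, 0.52.
- Follow-up SD 1.2 times the baseline SD: 1.31, 1.15, 1.03 at rho 0.3, 0.5, 0.7.
- Pain intensity: section 5 requires an average of at least 4 "on a 11-point numerical pain scale in the previous week", which narrows the baseline SD. With s the screened/unscreened baseline SD ratio (assumed 0.6-0.8) and r the correlation before screening, the ratio is 1 + s²(1 - r)/(1 + r): 1.19-1.35, 1.12-1.21, 1.06-1.11 at r 0.3, 0.5, 0.7. Physical function, which sets the sample size, has no such threshold.

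**4. Power (noncentral t, d = 0.65), unadjusted v adjusted.** Per-arm numbers: 50 as stated; 200/3 × 0.9 = 60; 90 × 0.9 = 81.

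| per arm | d on change SD | d on endpoint SD, rho 0.3 | rho 0.5 | rho 0.7 |
|---|---|---|---|---|
| 50 | 90% v 94-98% | – | – | – |
| 60 | 94% v 97-99% | 85% v 96% | 94% v 98% | 99.5% v 99.9% |
| 81 | 98% v 99% or more | 93.5% v 99% or more | 98.4% v 99% or more | over 99.9% on both |

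In the first column, the adjusted range covers rho 0.7 down to 0.3. Needed per arm for 90% power: on the change SD, 51 v 34-44; on the endpoint SD, 71 v 47, 51 v 39 and 31 v 27 at rho 0.3, 0.5 and 0.7.

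**5. Quadratic through baseline.** Assume a between-group difference of 0 at baseline, 0.65 at 1 month and 0.585 (0.9 × 0.65) at 12 months, with three decline shapes and ten covariance structures, after 4 weeks of treatment. Project this onto 1, t, t² over the six listed visits.

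| share of true difference | 1 month | 12 months |
|---|---|---|
| fitted change from baseline | 33-45% | 58-88% |
| fitted difference at the visit | 49-64% | 87-98% |

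The fitted peak falls about 6-9 months after treatment. A quadratic over follow-up visits from 1 month onward returns 97-100% at 1 month and 100-102% at 12.

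**The case against.** The strongest reply is that a difference in change from a mixed model is a standard, valid primary analysis. Type I error is unaffected, the stated power reproduces, and nothing in section 7c is wrong on this point. That stands: this is about efficiency.

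The gain can also be small. With the 270 enrolled in section 4, unadjusted power is at least 93.5% on either SD over rho 0.3-0.7. At rho 0.7 and 60 per arm the endpoint-SD comparison is 99.5% v 99.9%. That stands too, and since the documents do not settle 200 against 270, both are shown.

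The covariate clause could be read to include the baseline score. But it is conditional, and a baseline main effect in a model that still has baseline in the response would not change the interaction. The identity with raw change does assume categorical visits and complete data, which the plan does not state; otherwise it is approximate.

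On the quadratic, the bracketed list may only give measurement times, and the same sentence could mean change from baseline as the response. The shares depend on which fitted quantity is reported. Biomarkers at 1 month are examined separately, and model diagnostics are planned. All of this limits the point. For clinical outcomes, baseline as a fitted visit is only inferred, and section 7c calls the 12-month follow-up analysis exploratory.

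**Conclusion.** The point holds as an improvement in precision. On a categorical-visit reading, the primary contrast is essentially the raw change from baseline. With equal SDs its variance exceeds that of the adjusted contrast for any rho below 1, by 18% to 54% over the assumed range 0.7 to 0.3, and by less for pain intensity. The absolute size rests on rho, on which SD underlies 0.65, and on whether 200 or 270 are enrolled.

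A reader might infer that the primary analysis is biased or the trial underpowered. The documents do not support that. The contrast is unbiased, and the 90% reproduces directly on the change SD. The 85% at 60 per arm arises only if 0.65 is on the endpoint SD, rho is near 0.3 and enrolment is 200.

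A reader might also infer that the quadratic distorts the primary result, or that biomarker effects will be understated by a known amount. Neither follows. The 1-month primary contrast does not use that curve. The understatement needs baseline to be a fitted visit and biomarkers to change quickly and then hold, which is an assumption; the pilot pattern cited is for pain.

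**What to change.** **Primary model.** Suggested wording: Post-baseline scores are the response, with fixed effects for group, visit (categorical), group-by-visit, baseline score and baseline-by-visit. Covariance is unstructured over post-baseline visits up to 1 month; if this does not converge, random intercept plus AR(1). The primary estimates are APA minus CG-1 and APA minus CG-2 at the 1-month visit.

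Keeping baseline as an outcome with arm means constrained equal is an acceptable alternative, though not an exact equivalent under AR(1) or with missing data. Adding baseline only as a main effect while it stays in the response is not enough.

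**Sustained-effect models, clinical and biomarker.** Use categorical visits, or a curve over follow-up visits from 1 month onward with baseline as a covariate.

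**Clarification only.**
- Reconcile the blood time points (7 in the study-design text of section 4, 10 in its blood-sample paragraph, 6 in the Aim 2 model) and say which enter.
- State whether AR(1) runs on visit order or on months; actual months suit unequal spacing.
- State which visits enter the responder model and that the 1-month group odds ratios are reported.

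**Cost.** SAP wording only; no new data. On the Abstract's schedule there are 5 post-baseline visits to 1 month (4 weekly plus 1 month), so the unstructured covariance has 5 × 6/2 = 15 parameters. It is not proposed for the 12-month models.

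### The 30% responder model inherits group-by-time from baseline as its target, which is not the group difference in responders at 1 month and cannot be estimated if baseline rows are included

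*Combined protocol and SAP*

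**What the plan says.** All of the relevant text is in section 7c, in the analysis plan for aim 1.

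- **Timing.** "The primary outcomes are measured at 1-month post-completion of treatment".
- **Continuous outcomes.** A mixed model is used, with the purpose of "comparing the differences in the change in the outcomes from baseline to one month among the three groups". Its target is named in the next sentence: "The group-by-time interaction is the main parameter of interest". The text then adds adjustment for covariates, a subject random effect and an AR(1) structure.
- **Responder definition.** "a cut point of 30% improvement for primary outcomes will be used for responder analysis". This is introduced as an addition to the report of mean changes.
- **Responder model.** "we will adopt a generalized logistic mixed model" and it is to be fitted "with the same fixed and random effects and AR(1) covariance structure".
- **Longer follow-up.** By the same approach, "analyses will be conducted using the monthly data through 12 months to explore the maintenance of the effect over time", with quadratic time terms.

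The section does not say which records enter the responder model, which parameter is its target, or what is done if it does not converge. It promises model diagnostics for both models in general terms.

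**The concern.** A continuous score has a real value at baseline, so group-by-time from baseline to one month is a sensible measure of the difference in change. Responder status is different. It is already a statement about change since baseline, and at baseline it is 0 for everyone in every arm, whatever the data. Carrying the same fixed effects over therefore subtracts a baseline log odds ratio that does not exist.

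At stake is the pre-specification of the individual-level analysis of all three primary outcomes (pain intensity, pain interference, physical function). If the written model fails, or returns a parameter that answers another question, the replacement would be chosen after the data are seen.

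**Working it through.** **The plan's own figure.** Section 7c states that with 50 per group "we will be able to achieve 90% power to detect an effect size of .65". The usual formula gives n = 2(1.960 + 1.282)² / 0.65² = 49.7, so 50 per group, with power 0.901. The figure reproduces. It concerns the continuous outcomes; the plan gives no responder rates and no power for the responder analysis.

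**Inputs for the check.**
- Group size at 1 month: 200 enrolled less 10% lost = 180, or 60 per group (section 7c).
- Baseline responders: 0/60 in each group. This follows from the definition.
- 1-month responders: 33/60 (APA), 18/60 (CG-1), 15/60 (CG-2). These are **assumptions** for illustration.

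**Reading A: baseline rows are included.** The fixed part is logit P = intercept + group + time + group×time. The interaction for CG-1 against APA is

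[logit p(CG-1, 1 month) − logit p(CG-1, baseline)] − [logit p(APA, 1 month) − logit p(APA, baseline)].

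Both baseline logits are minus infinity, so their difference is undefined. Newton-Raphson on the fixed effects shows this:

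| Iterations | Intercept | Time effect | SE of each interaction term |
|---|---|---|---|
| 5 | −6.2 | 6.4 | 2.5 |
| 10 | −11.2 | 11.4 | 30 |
| 15 | −16.2 | 16.4 | 365 |
| 20 | −21.2 | 21.4 | 4,451 |
| 25 | −26.2 | 26.4 | about 54,000 |

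The exact values depend on where a fit that never converges is stopped. Only the divergence matters.

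The data do not fix the interaction either. Baseline logits (APA, CG-1, CG-2) of (−20, −20, −20), (−20, −25, −30) and (−30, −25, −20) all give a baseline log-likelihood of 0 to six decimals. The implied CG-1 interactions are −1.05, +3.95 and −6.05. Software may print −1.05 because all arms start from the same value, but that is a by-product of the starting point.

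A likelihood-ratio test does not help. Removing the interaction leaves the maximised log-likelihood at −111.68 in both models, a statistic of 0, because the group main effect absorbs the whole 1-month difference. A random intercept or AR(1) term does not help, because the baseline records carry no variation.

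**Reading B: post-baseline visits only.** The interaction between the end of treatment and 1 month is log OR(1 month) − log OR(end of treatment). It can be estimated. But if the APA against CG-1 odds ratio were 2.85 at both visits, it would be log 2.85 − log 2.85 = 0. A constant benefit would appear as no effect on the parameter named as being of main interest.

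**The quantity wanted.** Using the 1-month records alone:
- CG-1 against APA: log OR = log(18/42) − log(33/27) = −0.847 − 0.201 = −1.05. SE = √(1/33 + 1/27 + 1/18 + 1/42) = 0.38. The odds ratio for APA is 2.85.
- CG-2 against APA: log OR = log(15/45) − log(33/27) = −1.099 − 0.201 = −1.30. SE = √(1/33 + 1/27 + 1/15 + 1/45) = 0.40. The odds ratio for APA is 3.67.

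The same assumed data thus give a finite, usable estimate once the target is the group contrast at 1 month.

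**The case against.** The case for leaving the text alone has four parts.

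1. **The baseline row is inferred.** No sentence places it in the responder model. In section 7c the term fixed effects is attached to the demographic and clinical covariates, so the inherited effects could be read as those alone. For aim 2 the plan recodes change in a biomarker as 1 or 0, a variable with no baseline row. This is fair, and it is why the point is put under two readings. It does not supply a target: if the interaction is not inherited, the responder model has no stated parameter of interest.

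2. **A post-baseline model can be fitted.** A reader might infer that the responder analysis cannot be fitted on any reading. The documents do not support that. The abstract describes weekly outcomes during the intervention, Table 4 lists an assessment at the end of treatment, and the smartphone prompts are daily. In simulations with assumed rates (50 per arm, 60 datasets per setting, 2 or 5 post-baseline visits), a marginal AR(1) logistic model fitted by GEE always converged, with a mean SE of 0.44 for the 1-month group log odds ratio. GEE is not the planned mixed model, but it shows that the data carry the contrast. This objection stands in full, and what remains is Reading B: the model fits, but its interaction is not the 1-month effect.

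3. **The analysis is supplementary.** A reader might infer that the plan's whole judgement of clinical importance depends on it. It does not. The responder analysis comes in addition to mean changes, and no sample size rests on it. This stands.

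4. **Diagnostics would expose the failure.** A reader might infer that a real difference would be reported as non-significant. That is only one possible outcome; a standard error in the hundreds or thousands would be noticed. This stands too, but the plan names no fallback, so the repair would be unplanned.

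**Conclusion.** The point holds in a limited form. Under either reading that keeps the inherited interaction, it is the wrong target for the responder analysis: with baseline rows in the baseline-to-one-month model it has no finite estimate and no usable test, and with post-baseline visits only it measures change in the group difference over follow-up.

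The separation follows from the responder definition and does not depend on the assumed rates. Those rates, and the fit of the fixed effects alone, serve only to illustrate it. That baseline rows enter the model is an inference from the inherited specification.

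The practical consequence is probable non-convergence or a repair chosen after the data are seen, in a supplementary analysis of the three primary outcomes. The primary mean-change analysis and the sample size are untouched. The text should be changed, but the trial's main conclusion does not depend on it.

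**What to change.** Replace the sentence on the responder model in section 7c with text to this effect:

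*Responder status (at least 30% improvement from the participant's own baseline) is defined and modelled at post-baseline visits only. The target is the odds ratio between APA and each comparison group at 1 month post-treatment, adjusted for the baseline score of that outcome.*

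Then choose one estimation method in advance:

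- logistic regression on the 1-month records, with no random effect or AR(1) term, since each participant has one record; or
- a post-baseline repeated-measures logistic model with group, visit and group-by-visit, from which the 1-month group contrast is reported. This also uses earlier records of the roughly 10% expected to be lost by then.

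For the 12-month exploration, report the group odds ratio at each visit.

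The cost is wording only. No new data, visits or participants are needed.

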Our team's pilot data shows that using APA in older adults with cLBP resulted in 40% less pain one day after starting APA. We found that a four-week treatment achieves even greater pain relief (44% reduction) as well as improved function, both of which are maintained at the one-month follow-up. Blood-level reduction in pro-inflammatory cytokines (e.g., IL-β) and calcitonin gene-related peptide (CGRP) and increased anti-inflammatory cytokines (e.g., IL-4) suggest APA impacts neural-immune signaling. Further, we have developed and piloted a smartphone application (app) of ecological momentary assessment (EMA) to collect real-time cLBP outcomes associated with APA, with good usability reported by patients, which limits recall bias. Pilot data combined with the feasibility of implementing APA widely in clinical practice provide the impetus for pursuing the next stage of research—evaluating the sustained efficacy of APA for cLBP.

We propose a randomized controlled trial to: (1) determine the efficacy of APA in relieving cLBP, and (2) examine the physiological impact of APA on cLBP in 200 adults 65 years or older (n=200 will be able to provide 90% power to detect 30% function improvement). To address possible placebo effects of treatment (i.e., point specificity) and nonspecific psychological factors (i.e., treatment beliefs, expectations, and patient-provider relationship), we will use a three-group design: (1) APA (active ear points relative to cLBP), (2) Comparison Group (CG)-1 (non-active points, not related to cLBP), (3) CG-2 (enhanced educational control). Our EMA app will be used to monitor APA adherence and capture daily momentary cLBP outcomes and analgesic use. Outcomes will be measured via EMA, weekly during intervention, 1-month after completion of APA (primary endpoint), and monthly follow-up up to 12-months to assess sustained effects. Our approach addresses the mission of the National Institute on Aging, the standardized research approach on cLBP suggested by the NIH Pain Consortium Research

PROTOCOL NUMBER: 21-1059

IRB APPROVAL DATE: 02/04/2022

Task Force and the Surgeon General's challenge to limit prescription of opioids by providing a nonpharmacological strategy.

2. Objectives (include all primary and secondary objectives)

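### The 12-month and biomarker models rest on one subject-plus-AR(1) covariance with no robust fallback; if response varies between people, and more so under APA, intervals for change from baseline can be too narrow

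*Combined protocol and SAP*

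**What the plan says.** Section 7c, on the Aim 1 analysis, sets the covariance: "Random effects from subject heterogeneity and temporal autocorrelation with the first-order autoregressive (AR(1)) covariance structure will be used to model the repeated measurements". It names no separate variances by arm, so the structure is read here as common to all three. It is then carried forward: "Using the approach outlined above, analyses will be conducted using the monthly data through 12 months". The mean in that model is quadratic: "Quadratic terms will be included in the model to allow for non-linear change across time".

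For the sustained biomarker effect, the Aim 2 text says "we will use the approach described in Aim 1 using linear mixed models with quadratic terms", at "baseline, 1, 3, 6, 9, 12 months".

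The only safeguard is that "violation of assumptions will be detected by corresponding model diagnostics". No action is attached to a violation, and no alternative covariance or robust standard error is named.

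Table 1 in section 3 gives the pilot change in pain for cLBP: mean -3.53 (SD 2.66) under APA and -0.77 (SD 1.41) under sham. The Abstract describes early gains in pain and function, "both of which are maintained at the one-month follow-up". Section 5 requires pain of at least 4 at entry, which restricts the range at baseline only.

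**The concern.** A subject effect plus stationary AR(1) gives every visit the same variance. It also makes baseline as correlated with the next visit as any two neighbouring follow-up visits are with each other. If people differ in how far they move after baseline and then hold their new level, baseline is less correlated with follow-up than follow-up visits are among themselves. Follow-up visits dominate the fit, so the model can understate the variance of change from baseline. If the spread is larger under APA, a variance pooled over arms understates it again for APA against a comparison group.

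At stake are the sustained-effect results, which are part of Aim 1 and the stated reason for enrolling 200 rather than 150, and the long-term biomarker results. Both could look more precise than they are.

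**Working it through.** **1. The plan's own figure.** Section 7c gives 50 per group for d = 0.65, 90% power and two-sided 0.05. n = 2(1.960 + 1.282)²/0.65² = 21.02/0.4225 = 49.7, so 50. Then 150/(1 - 0.25) = 200. Both reproduce. The plan gives no figure for covariance or coverage.

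**2. What the structure leaves out.** With residual variance σ² and autocorrelation ρ, the model has Var(y_k - y_0) = 2σ²(1 - ρ^k), because the subject effect cancels. If people also make a lasting personal step after baseline with SD τ, the true variance is 2σ²(1 - ρ^k) + τ². A shift shared by everyone adds nothing; only its spread does. On 14 monthly occasions (baseline, end of treatment, 12 follow-ups) there are 14 × 13/2 = 91 visit pairs. Only 13 of them (14%) involve baseline, so the fit says little about τ.

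**3. Pilot anchor (pain).** Take the sham change as all residual: σ² = 1.41²/2 = 0.994 if residuals are uncorrelated. Put the excess in the APA arm: τ² = 2.66² - 1.41² = 7.076 - 1.988 = 5.088, so τ = 2.26. Assumed: stable subject variance 2, CG-2 like sham, and monthly residual correlation from 0 to about 0.8 with σ² reset so that the sham SD of change stays 1.41.

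**4. Arm pooling alone.** Average variance of change over three equal arms = (7.076 + 2 × 1.988)/3 = 3.684. SE ratio for APA against one comparison group = √[2 × 3.684/(7.076 + 1.988)] = 0.902. Coverage = 2Φ(1.96 × 0.902) - 1 = 92.3%. This would remain with a common unstructured matrix.

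**5. Fitted results, monthly schedule.** The planned covariance was fitted at its large-sample Gaussian optimum. Model SE was divided by true SE for the between-arm change from baseline, and coverage = 2Φ(1.96 × ratio) - 1. This measures width only and assumes complete data.

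| Mean model | Assumptions | First follow-up month | Month 12 |
|---|---|---|---|
| Quadratic (planned) | Pilot-anchored, uncorrelated residual | ratio 0.77, 87.0% | ratio 0.88, 91.5% |
| Quadratic (planned) | Pilot-anchored, range of residual correlations | about 87-90% | about 91.5-94% |
| Quadratic (planned) | Equal arms, τ = 0.7 baseline SDs, residual correlation 0.5 | ratio 0.88, 91.6% | ratio 0.97, 94.1% |
| Quadratic (planned) | Equal arms; SD 2.0, or 1.5 then 2.3; baseline correlation 0.3-0.6; adjacent follow-up correlation 0.68 or 0.78 | 91-98% | 94-97% |
| Visit-specific means | Pilot-anchored | about 73-83% | 83% (uncorrelated residual) |
| Visit-specific means | No person-specific step | 95.0% | 95.0% |

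The equal-arm range belongs to its stated assumptions; a more variable step would lower it. Adding a random slope hardly changes the early contrast (83% pilot-anchored, visit-specific means).

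**6. Simulation check.** 400 runs with 50 per arm, equal arm variances and visit-specific means gave 87.8-92.2% mean coverage for the planned covariance and 94.2-95.7% for unstructured.

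**7. Biomarkers.** Intervals between the labelled visits are 1, 2, 3, 3 and 3 months. If months run from the end of the 4-week treatment, the first is nearer 2. Either way they are unequal, and AR(1) by visit order would treat them as equal. The documents give no biomarker SD or correlation. Borrowing pain assumptions under the quadratic gives anything from 87.6% (pilot-anchored, month 1) to about 97%, which only shows that the size is unknown.

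**8. Baseline and 1 month only.** With equal arm variances the ratio is 1.00 and coverage 95.0%. The subject, residual and AR(1) parameters cannot then be separated, but the standard error is unaffected. With the pilot SDs it is 92.3%, all of it from step 4.

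**The case against.** The strongest reply is that the plan specifies a quadratic mean, under which a fitted change borrows from every visit and is less exposed than a raw visit difference. This stands. A reader might infer month-1 coverage of 83-92% from fits with a free mean at each visit, but that is not the planned model.

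A reader might also blame the early fall in pain itself. Those figures are means, and a mean shift does not alter the covariance. Only variation in the shift matters, and the evidence for it is two pilot SDs. At an assumed SD of 2.0, the sham SD implies a baseline-to-follow-up correlation of 1 - 1.988/8 = 0.75, where little is lost. The APA SD implies 1 - 7.076/8 = 0.12. So the case rests on variation between people and between arms, not on 2.66 alone.

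A third tempting reading is that the biomarker results are shown to be falsely precise. Pain SDs and a pain entry rule say nothing about cytokine covariance. Nor does the plan say that AR(1) is indexed by visit order, or that the subject effect is only an intercept.

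The 12-month analysis is labelled exploratory, which lowers the stakes. Diagnostics are planned, but with no stated consequence they are only a partial safeguard.

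A quadratic also cannot follow a step: in these fits a mean step of 1 appears as 0.26-0.41 at 1 month and 0.37-0.72 at month 12. That is a separate bias which better standard errors do not cure.

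**Conclusion.** The point holds in a limited form. One covariance, common to all arms, is carried into the monthly and biomarker models without a robust standard error or a fallback. If response varies as the pilot pain SDs suggest, nominal 95% intervals for monthly pain cover about 87-90% at the first follow-up month and 91.5-94% at month 12 under the planned quadratic. With equal arm variances coverage is about 91-98%, often near nominal. Visit-specific means would make the early shortfall worse.

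These figures rest on assumed residual correlations, on CG-2 resembling sham and on complete data; the documents give no repeated-measures covariance. For biomarkers the firm point is only the unequal spacing. The documents do not support extending the AR(1) problem to the primary 1-month comparison if it is fitted on baseline and 1 month alone.

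**What to change.** In section 7c, for the 12-month and biomarker models:

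- Base inference on small-sample-corrected empirical (sandwich) standard errors, whatever the working covariance.
- Alternatively, use arm-specific unstructured covariance where the number of visits allows. Six visits need 6 × 7/2 = 21 parameters per arm; fourteen need 14 × 15/2 = 105, against about 200/3 = 67 people per arm. This suits the biomarker model and not the monthly one.
- Do not rely on a common unstructured matrix alone, because it leaves about 92.3% coverage if the arms differ as in the pilot.
- Index any autoregressive term by actual time (continuous-time or spatial power).
- State what follows if the diagnostics show a violation.

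The cost is plan wording, model options and slightly wider intervals. No new data, visits or participants are needed.
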